5.4.2.2 Time to first confirmed relapse

The time to first confirmed relapse (in days) is defined as [Date of first confirmed relapse – Date of randomization + 1] in days.

Subjects without any confirmed relapses will be censored at the EOS date, and the time is defined as [Date of EOS – Date of randomization + 1] in days.

Derivation of confirmed relapses from randomization up to EOS is detailed in Section 5.4.1. Among these confirmed relapses, the earliest relapse start date is the ‘Date of first confirmed relapse’. For analysis the variable is displayed in weeks: variables in days divided by 7.

5.4.2.3 Number of combined unique active lesions (CUAL) up to EOS

The cumulative number of CUAL from baseline to EOS is calculated as the sum of new T1 Gd+ lesions and new or enlarging T2 lesions without Gd enhancement on T1 at all post-baseline MRI visits up to EOS.

MRI scans are scheduled at Baseline, and every 24 weeks thereafter, i.e., at the visits at Week 24, Week 48, Week 72, Week 96, Week 120, Week 144 Visit and at the EOT visit. For subjects who prematurely discontinue treatment, an additional premature EOT visit MRI is scheduled. Unscheduled MRI scans may be conducted in addition.

MRI data are read centrally and provided to the sponsor.

To account for varying observation time, e.g., in case of premature study withdrawal or missing MRI assessments, the analysis will be adjusted by: Time up to the last MRI (years) = (Date of last MRI considered in derivation of CUAL – Randomization date + 1) / 365.25 days.

Rationale: Due to the fact that MRI scans are scheduled every 24 weeks, the CUAL count is expected to be mainly driven by new T2 lesions. The number of T2 lesions is expected to increase with observation time. In contrast, in studies where MRI scans are scheduled more regularly, the CUAL count is mainly driven by new T1 Gd+ lesions which are expected to increase with the ‘Number of MRI scans’ conducted. Also, in this study, there is an additional MRI following premature treatment discontinuation which can occur at any time, and which does not occur per

the planned schedule for any subjects and so the ‘number of MRI scans’ is not necessarily expected to be a good approximation of the observation time.

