2.1.1 Periods

The study consists of the following protocol defined periods:

- **Pre-randomization period** starts with signature of the Informed Consent Form (ICF) and ends with the subject's randomization and lasts up to 45 days (per screening attempt). Subjects can be re-screened once. It includes Visit 1 (Screening), Visit 2 (Baseline) and the pre-dose assessments of Visit 3 (Day 1).
- **Treatment period** starts on the day of randomization immediately after the first dose of study drug intake (Visit 3–Day 1 of the study). The double-blind treatment period has a variable duration from a minimum of 60 weeks (for the last subject randomized) to a maximum of 156 weeks (3 years) for the first subjects randomized in the trial. Average duration is expected to be approximately 2 years. It includes a randomization visit, visits at 2, 4, and 12 weeks after randomization, and 12-weekly visits thereafter until 60 weeks after the randomization of the last subject or 156 weeks of treatment (whichever occurs first). The treatment period consists of a titration and a maintenance phase.
 - A 2-week titration scheme is implemented on Day 1 (or at re-initiation following a treatment interruption of more than 3 days) to reduce the first-dose effects of ponesimod [see [Table 1](#)]. During the up-titration period, one tablet of ponesimod 2, 3, 4, 5, 6, 7, 8, 9, or 10 mg (or matching placebo) will be taken orally once daily.
 - The titration phase is followed by the maintenance phase with one tablet of ponesimod 20 mg (or matching placebo) administered orally once daily in the morning (from Day 15 to EOT).
- **Post-treatment period** starts immediately after the last dose of study treatment and ends when End-of-Study (EOS) visit has been completed. It comprises the post-treatment safety follow-up period and if applicable, is followed by the PTOP.
 - **Post-treatment safety follow-up period**
All subjects will enter the safety follow-up period which lasts for at least 30 days after the last dose of study treatment and includes a safety follow-up visit approximately 30 days after the last dose of study treatment (FU visit). Subjects participating in the lymphocyte subset sub-study will have an additional follow-up visit approximately 7 days after the last dose of study drug (FU7d visit).
 - **Post-treatment observation period**

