5.4.2.3.1 Derivation details

The central reader provides the ‘Number of new T1 Gd+ enhancing lesions’ (variable T1GdNew_R) and ‘Number of new T2 lesions without Gd enhancement’ (variable T2New_R) at a visit as compared to the last scheduled MRI scan (with premature EOT visit being considered a scheduled MRI). At the first scheduled post-baseline visit comparison is made to baseline (with baseline defined as the Baseline Visit 2, or Visit 2 - 2nd attempt if available [see Section 5.4.3] for details and a rationale).

Cumulative CUAL from baseline to EOS is derived as the sum of ‘Number of new T1 Gd+ enhancing lesions’ and ‘Number of new T2 lesions without Gd enhancement on T1’ across all post-baseline MRI visits up to up to EOS irrespective of whether a visit is conducted during PTOP or not.

As only the number of new lesions as compared to the last scheduled visit is recorded by the central reader, lesions are not expected to be double counted when summing over scheduled visits.

In the rare event that the baseline MRI visit is conducted after randomization date, the variable is derived in the same way, i.e., based on the nominal visit. Note that effectively the derived variable then covers a period starting slightly after randomization. If the baseline MRI is missing, new or enlarging T2 lesions as compared to baseline cannot be assessed and consequently the endpoint is considered missing. The baseline MRI is considered missing if presence of T1 Gd+ lesions at baseline is missing.

For subjects with at least one unscheduled post-baseline MRI scan, care needs to be taken in the derivation to avoid double counting of lesions and the following algorithm applies:

- If a subject has an unscheduled MRI which is the last available MRI in the time period considered: Include that last unscheduled MRI when deriving CUAL in the same way as for scheduled visits.
- If a subject has an unscheduled MRI which is not the last available MRI for the subject: Do not include that unscheduled MRI. Rationale: New / enlarging lesions at the unscheduled MRI as well as at the later scheduled MRI are reported in reference to the previous scheduled visit. Including both may result in double counting.

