5.4.3 Exploratory MRI efficacy variables

MRI data are provided from a central reader.

Baseline

The central reader defines the result from ‘Visit 2 - Baseline’ as baseline (or ‘Visit 2a - Baseline 2nd attempt’ if available) and uses that Baseline visit as a reference in derivations of various variables (e.g., new or enlarging T2 lesions).

For analysis, baseline for MRI variables is defined in the same way, i.e., Visit 2 unless Visit 2a is available. In the unexpected case a Visit 2 scan is conducted after randomization, it is still considered as baseline.

MRI at post-baseline scheduled visits - visit windowing

MRI variables at scheduled visits are based on the result from the corresponding nominal visit (or from a re-mapped premature EOT visit [see Section 11.3]). In case of missing results, MRI results from an unscheduled visit can be re-mapped to a scheduled visit if conducted during the time window specified in Section 11.3. Care needs to be taken however in derivation of cumulative variables where occasionally unscheduled MRIs are not included, as per the respective derivation details.

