5.4.3.3 Number of new or enlarging T2 lesions

New or enlarging T2 lesions as compared to the previous scheduled visit are recorded by the external reader in two distinct categories: ‘Number of new or enlarging T2 lesions without Gad. enhancement on T1’ (T2New_R) and ‘Number of new or enlarging T2 lesions with Gad. enhancement on T1’ (T2NewGd_R) at a visit as compared to the previous scheduled visit. The sum of both is the ‘number of new or enlarging T2 lesions’ at that visit compared to the previous scheduled visit. For subjects with missing baseline MRI, the number of new or enlarging T2 lesions from baseline cannot be assessed and the endpoint is considered missing. The baseline MRI is considered missing if presence of T1 Gd+ lesions at baseline is missing.

The cumulative number of new or enlarging T2 lesions from baseline to Week 24, Week 48, Week 72, Week 96, EOT and EOS is calculated as the sum of lesions at all post-baseline MRI visits up to the applicable MRI visit.

The cumulative number of new or enlarging T2 lesions from baseline up to the applicable MRI visit is derived as the sum of the ‘number of new or enlarging T2 lesions’ at all scheduled post-baseline MRI visits, including premature EOT visit if applicable (irrespectively if a visit is conducted during PTOP or not), for subjects with only scheduled post-baseline MRI scans.

For subjects with at least one unscheduled post-baseline MRI scan, care needs to be taken in the derivation to avoid double counting of lesions and the following algorithm applies:

- If a subject has an unscheduled MRI which is the last available MRI in the time period considered: Include that last unscheduled MRI when summing over ‘number of new or enlarging T2 lesions’ in the same way as the scheduled visits.
- If a subject has an unscheduled MRI which is not the last available MRI for the subject in the time period considered: Do not include that unscheduled MRI. Rationale: New / enlarging lesions at the unscheduled MRI as well as at the later scheduled MRI are reported in reference to the previous scheduled visit. Including both would result in double counting.

To account for varying observation time the analysis will be adjusted by: Time up to the last MRI (years) = Date of last MRI considered in derivation – Randomization date + 1 divided by 365.25 days.

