1.5 Pregnancy and Contraception

Condition	Type	Identifier	Source/Instructions	Additional information expected?	Important PD
Woman of childbearing potential with a negative serum pregnancy test at Visit 1 (Screening) and a negative urine pregnancy test at Visit 2 (Baseline) performed < 21 days apart	M	PD_MM.009	Monitor PD / eCRF [Demographics] [Urine Pregnancy Test] [Central Lab] e.g., serum and urine pregnancy tests performed 20 days apart		No
Contraceptive methods requirements for WOCBP as described in protocol section 4.5.2 not followed by subject	M	PD_MM.219	Monitor PD / eCRF [Contraceptive Methods] e.g., hormonal contraceptive started less than 30 days prior to randomization Note: To be used only if deviation occurred prior to randomization. If deviation occurred after randomization, use code MM.138		No

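### CUAL and T2 lesions are counted from the baseline MRI, but exposure time starts at randomization, so the rates per subject-year are modestly overstated, most at Week 24

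*SAP*

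**What the plan says.** Section 5.4.2.3 adjusts the cumulative CUAL count for time up to the last MRI, defined as "Date of last MRI considered in derivation of CUAL – Randomization date + 1) / 365.25 days". Section 5.4.3.3 does the same for new or enlarging T2 lesions: "Date of last MRI considered in derivation – Randomization date + 1 divided by 365.25 days". These times are the offsets, and the denominators of the raw rates per year, in 9.7.3 (CUAL up to EOS), 9.8.1 Number of CUALs (Weeks 24, 48, 72, 96 and EOT) and 9.8.3 (T2 lesions at the same timepoints and EOS).

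The count has a different origin. Section 5.4.2.3.1 states: "At the first scheduled post-baseline visit comparison is made to baseline". Section 5.4.3 fixes the baseline scan as "Visit 2 unless Visit 2a is available". Section 2.1.1 places Visit 2 in the pre-randomization period, which "ends with the subject's randomization and lasts up to 45 days (per screening attempt"). That period starts at consent, and on its contents the section says: "It includes Visit 1 (Screening), Visit 2 (Baseline) and the pre-dose assessments of Visit 3 (Day 1").

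Section 5.4.2.3.1 recognises that the counting period and the randomization date can differ, but only for the rare case of a baseline scan after randomization. It corrects neither direction.

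**The concern.** Sections 4.1 and 5.4.2.3 abandon the protocol's number-of-scans offset because lesion counts grow with observation time. The time chosen in its place is not the interval over which lesions are counted. The numerator runs from baseline MRI to last MRI, the denominator from randomization to last MRI. A baseline scan before randomization is the intended case: the deviation list in Attachment 1, section 1.2, treats a pre-randomization MRI done after randomization as an important deviation. The mismatch therefore has a usual direction.

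At stake are the per-arm lesion rates per subject-year, which are named outputs, and their pattern over the planned timepoints. The relative error depends on follow-up length, so rates at Week 24 and Week 96 are not comparable even if the true rate is constant.

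**Working it through.** The SAP states no expected lesion rate, so there is no figure of its own to reproduce.

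**Formula.** Let T be days from randomization to last MRI as the SAP defines it, g the days from baseline MRI to randomization, and λ a constant lesion rate. The expected count is about λ(T + g), ignoring the one-day convention. The SAP divides by T, so the relative overstatement is (T + g)/T − 1 = g/T.

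**Range for g.** The SAP does not give it.
- The 45 days in 2.1.1 cover the whole period from consent to randomization, and Visit 1 precedes Visit 2 within it. For this gap, 45 days is only an outer bound.
- Attachment 1, section 1.5, lists as a deviation, for women of childbearing potential, a serum test at Visit 1 and "a negative urine pregnancy test at Visit 2 (Baseline) performed < 21 days apart". If the scan is done on the day of that urine test, the gap without a deviation is at most 45 − 21 = 24 days.
- I therefore use 14 and 24 days as an assumed working range, with 45 as the extreme.

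**Overstatement g/T**, with T at the nominal days of Table 7 (Day 85 is the earliest premature-EOT scan that Table 7 maps to Week 24):

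| Last MRI | T (days) | g = 14 | g = 24 | g = 45 (extreme) |
|---|---|---|---|---|
| Day 85 | 85 | 16.5% | 28.2% | 52.9% |
| Week 24 | 169 | 8.3% | 14.2% | 26.6% |
| Week 48 | 337 | 4.2% | 7.1% | 13.4% |
| Week 96 | 673 | 2.1% | 3.6% | 6.7% |

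**Artificial decline.** With a constant true rate and g = 24, the reported rate would fall from 1.142 to 1.036 times the truth between Week 24 and Week 96. That is 1 − 1.036/1.142, about 9%. With g = 14 it is 1 − 1.021/1.083, about 6%.

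**Up to EOS.** I assumed 68 subjects per arm, entry staggered over 2.5 years, 15% withdrawal per year, a placebo rate of 2 lesions per year, a true rate ratio of 0.5 and dispersion 1.5. Mean T is then about 490 days. Total gap over total time, which is the error in the raw rate, is 2.8% (14 days), 4.9% (24 days) and 9.2% (45 days).

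Negative binomial fits to 200 simulated data sets per gap, with both offsets applied to the same data, gave these medians:

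| g | Placebo rate, SAP offset | Placebo rate, baseline-MRI offset | Rate ratio, SAP | Rate ratio, baseline-MRI |
|---|---|---|---|---|
| 14 | 2.02 | 1.95 | 0.509 | 0.511 |
| 24 | 2.16 | 2.02 | 0.515 | 0.516 |
| 45 | 2.24 | 1.98 | 0.556 | 0.557 |

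The model-based placebo rates differ by 2.02/1.95, about 4%, and 2.16/2.02, about 7%, for gaps of 14 and 24 days. This is slightly more than the raw rates because an overdispersed model gives short follow-ups more weight than their share of total time. The proportion of data sets with p < 0.05 was 0.73 against 0.74 at both 14 and 24 days. Comparisons within a row are informative; differences between rows carry simulation noise.

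**The case against.** The strongest reply is that this barely matters. Randomization is the common time origin for efficacy in the SAP (11.2.1). The gap precedes treatment assignment and is balanced in expectation, and the simulated rate ratio moves only in the third decimal. CUAL is a secondary endpoint analysed as exploratory (9.1.1, 9.7), and T2 lesions are exploratory. All of this stands, and it limits the point to the annual rates.

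The constant-rate assumption can also be questioned. A relapse between baseline EDSS and randomization excludes a subject (Attachment 1, section 1.4), which could lower lesion formation in the gap. Entry also requires active disease, which could raise it. The percentages are therefore approximate.

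Three stronger readings are tempting but are not supported:
- A reader might take 45 days as the lead between scan and randomization. It limits the whole period from consent. A longer gap than the working range is possible in some subjects, for instance men, or perhaps a re-screened subject who keeps the first scan, but the SAP shows nothing about how often.
- A reader might infer from the 8-week limit for EOT visits in section 2 that the early stop left many very short follow-ups. Those 8 weeks run from the termination decision, not from randomization. Enrolment began in March 2017 and the decision came on 26 November 2019, so follow-up ranges from short to long.
- A reader might expect the varying error to damage the treatment comparison through the offset weights or the dispersion. The simulation shows no material change in the ratio or in the rejection rate.

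**Conclusion.** The mismatch is wrong as written and worth correcting, but its effect is modest. Reported CUAL and T2 rates per subject-year are overstated by about g/T. For assumed gaps of 14 to 24 days this is about 8–14% at Week 24, 4–7% at Week 48 and 2–4% at Week 96. Up to EOS it is roughly 3–5% in the pooled raw rate, and a little more in the model-based rate under the assumed follow-up. Rates will appear to decline over the planned timepoints even if the true rate does not. Where a baseline scan falls after randomization, the error reverses and the rate is understated.

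The conclusion about treatment effect does not change. Lesions formed before randomization pull the ratio slightly towards 1 (from 0.50 to about 0.51–0.52 for 14 to 24 days in the simulation), and neither offset removes that. The sizes rest on an assumed gap, a constant lesion rate and, for EOS, an assumed entry and withdrawal pattern. The direction for the usual case rests only on the SAP's definitions.

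**What to change.** In 5.4.2.3 and 5.4.3.3, define the exposure time as (date of last MRI included − date of the baseline MRI used by the central reader) / 365.25. Use its logarithm as the offset, and the same time as the raw-rate denominator, in 9.7.3, 9.8.1 Number of CUALs and 9.8.3. This also handles baseline scans done after randomization. The T1 Gd+ analyses in 9.8.2 use the number of scans and need no change.

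If the randomization origin is kept for consistency, report the distribution of the gap by arm and add a sensitivity analysis with the baseline-MRI offset.

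The cost is one derivation line. It needs only the scan dates, with no new data collection. A sentence in the report should note that lesions formed before randomization remain in the count under either offset.

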5.4.2.3.1 Derivation details

The central reader provides the ‘Number of new T1 Gd+ enhancing lesions’ (variable T1GdNew_R) and ‘Number of new T2 lesions without Gd enhancement’ (variable T2New_R) at a visit as compared to the last scheduled MRI scan (with premature EOT visit being considered a scheduled MRI). At the first scheduled post-baseline visit comparison is made to baseline (with baseline defined as the Baseline Visit 2, or Visit 2 - 2nd attempt if available [see Section 5.4.3] for details and a rationale).

Cumulative CUAL from baseline to EOS is derived as the sum of ‘Number of new T1 Gd+ enhancing lesions’ and ‘Number of new T2 lesions without Gd enhancement on T1’ across all post-baseline MRI visits up to up to EOS irrespective of whether a visit is conducted during PTOP or not.

As only the number of new lesions as compared to the last scheduled visit is recorded by the central reader, lesions are not expected to be double counted when summing over scheduled visits.

In the rare event that the baseline MRI visit is conducted after randomization date, the variable is derived in the same way, i.e., based on the nominal visit. Note that effectively the derived variable then covers a period starting slightly after randomization. If the baseline MRI is missing, new or enlarging T2 lesions as compared to baseline cannot be assessed and consequently the endpoint is considered missing. The baseline MRI is considered missing if presence of T1 Gd+ lesions at baseline is missing.

For subjects with at least one unscheduled post-baseline MRI scan, care needs to be taken in the derivation to avoid double counting of lesions and the following algorithm applies:

- If a subject has an unscheduled MRI which is the last available MRI in the time period considered: Include that last unscheduled MRI when deriving CUAL in the same way as for scheduled visits.
- If a subject has an unscheduled MRI which is not the last available MRI for the subject: Do not include that unscheduled MRI. Rationale: New / enlarging lesions at the unscheduled MRI as well as at the later scheduled MRI are reported in reference to the previous scheduled visit. Including both may result in double counting.

5.4.3 Exploratory MRI efficacy variables

MRI data are provided from a central reader.

Baseline

The central reader defines the result from ‘Visit 2 - Baseline’ as baseline (or ‘Visit 2a - Baseline 2nd attempt’ if available) and uses that Baseline visit as a reference in derivations of various variables (e.g., new or enlarging T2 lesions).

For analysis, baseline for MRI variables is defined in the same way, i.e., Visit 2 unless Visit 2a is available. In the unexpected case a Visit 2 scan is conducted after randomization, it is still considered as baseline.

MRI at post-baseline scheduled visits - visit windowing

MRI variables at scheduled visits are based on the result from the corresponding nominal visit (or from a re-mapped premature EOT visit [see Section 11.3]). In case of missing results, MRI results from an unscheduled visit can be re-mapped to a scheduled visit if conducted during the time window specified in Section 11.3. Care needs to be taken however in derivation of cumulative variables where occasionally unscheduled MRIs are not included, as per the respective derivation details.

5.4.3.1 Number of CUALs

The cumulative number of CUALs from baseline to Week 24, Week 48, Week 72, Week 96 and EOT is derived in the same way as for CUAL from baseline to EOS [see Section 5.4.2.3], but only including MRI scans up to the applicable MRI visit (if missing, up to remapped equivalent) as applicable.

Note that if an unscheduled MRI becomes the last available MRI in the considered time period it is to be included in deriving the sum of lesions.

5.4.3.2 Number of T1 Gd+ lesions

The **number of T1 Gd+ lesions per visit** is derived as the sum of ‘number of new T1 Gad.-enhancing lesions’ (T1GdNew_R) + ‘number of persisting T1 Gad.-enhancing lesions’ (T1Gd_R) as provided by the central reader at that visit.

Handling of missing MRI results at scheduled visits follows the general rules for MRI data described in Section 5.4.3 above.

The **cumulative number of new T1 Gd+ lesions from baseline to Week 48** is derived as the sum of number of **new** T1 Gd+ lesions at all post-baseline MRI scans up to the Week 48 MRI visit. This includes premature EOT scans if available. It may include unscheduled scans if it is the last available scan, following selection of unscheduled MRIs as per derivation of CUAL [Section 5.4.2.3]. To account for a potentially varying number of scans contributing to the variable, the analysis will be adjusted by the ‘Number of MRI scans’ included in the derivation.

Note: The number of T1 Gd+ lesions at baseline is taken from the variable ‘Number of T1 Gad.-enhancing lesions at V2 – Baseline/Number of persisting T1 Gad.-enhancing lesions’ (T1Gd_R). At baseline new T1 Gd+ lesions are not available, thus no corresponding record is expected.

Note: T1 Gd+ lesions are assumed to not enhance for more than 12 weeks. This requires handling of data as follows:

- *If at a visit, number of persisting T1 Gd+ lesions are not recorded, the number of Gd+T1 lesions is the number of new T1 Gd+ lesions. Rationale: As per central reader processes*

persisting T1 Gd+ lesions are not assessed for subjects with scheduled MRIs scheduled more than 12 weeks apart (i.e., MRIs are scheduled every 24 weeks).

- *If at a MRI scan which is > 12 weeks (84 days) since the last previous scheduled MRI scan a persisting lesion count > 0 is recorded, these persisting lesions are considered implausible and therefore not to be considered in derivations of total T1 Gd+ counts.*

The cumulative number of new T1 Gd+ lesions from baseline will also be derived in the same way as described above for cumulative up to Week 48 for the following timepoints: Week 24, Week 72, Week 96, and EOT and EOS.

